# 5.1.15 The PsA Impact of Disease 12-Item (PsAID-12) Questionnaire

The PsAID-12 Questionnaire (Appendix N of Protocol) is a 12-item, self-administered questionnaire that reflects the impact of PsA from the perspective of the patient. It is composed of 12 physical and psychological domains. Each domain is rated from 0 to 10 with a different weighting. The total score is divided by 20.

Protocol Number: 20200058

Date: 07 February 2023 Page 27 of 67

[figure not shown]
Final PsAID-12 value = [ (PsAID1 (pain) NRS value (range 0-10) x 3)

- + (PsAID2 (fatigue) NRS value (range 0-10) x 2)
- + (PsAID3 (skin) NRS value (range 0-10) x 2)
- + (PsAID4 (work and/or leisure activities) NRS value (range 0-10)
- x 2)
- + (PsAID5 (function) NRS value (range 0-10) x 2)
- + (PsAID6 (discomfort) NRS value (range 0-10) x 2)
- + (PsAID7 (sleep) NRS value (range 0-10) x 2)
- + (PsAID8 (coping) NRS value (range 0-10) x 1)
- + (PsAID9 (anxiety) NRS value (range 0-10) x 1)
- + (PsAID10 (embarrassment and/or shame) NRS value (range 0-10) ×1)
- + (PsAID11 (social life) NRS value (range 0-10) x 1)
- + (PsAID12 (depression) NRS value (range 0-10) x 1)]/20

The final score has a range from 0 (best status) to 10 (worst status), with a cut-off  $\leq$  4 representing patient-acceptable symptom state. (Gossec, 2014).

If one of the 12 domains composing the PsAID is missing, it will be imputed by the mean value of the 11 non-missing NRS scores. If two or more of the domains are missing, the final PsAID score will be considered as missing.

Data resource: PsAID-12 is captured via tablets provided by ERT.

Protocol Number: 20200058 Date: 07 February 2023

[figure not shown]
Page 28 of 67

Protocol Number: 20200058 Date: 07 February 2023

Page 29 of 67

Protocol Number: 20200058 Date: 07 February 2023

# 5.2 Derivations of Safety Endpoints

Baseline definition for all safety endpoints is given in Section 5.3. Change from baseline is calculated as on-treatment value minus the baseline value. Handling of time points is described in Section 5.4.

Treatment-emergent Adverse Event

An AE is a treatment-emergent AE (TEAE) if the AE start date is

- on or after the date of the first dose of investigational product (IP) and no later than 28 days after the last dose of IP for subjects who have completed the study or have discontinued early by the time of database cut, or
- on or after the date of the first dose of IP for subjects who are ongoing at the time of database cut

Protocol Number: 20200058

Date: 07 February 2023

Page 31 of 67

If the treatment-emergent status of an AE is unclear due to a missing/incomplete start date, it will always be considered treatment-emergent, unless shown otherwise by data. Date imputation rules for partially missing AE start dates are described in Section 8.3.1

# 5.2.1 Treatment-emergent Adverse Events Leading to Drug Withdrawal, Leading to Drug Interruption, and Leading to Death, and Drugrelated Treatment-emergent Adverse Events

A TEAE leading to drug withdrawal is a TEAE for which the investigator indicates that the action taken with respect to IP is withdrawn permanently (action taken on AE eCRF is recorded as "DRUG WITHDRAWN"). A TEAE leading to drug interruption is a TEAE for which the investigator indicates that the action taken with respect to IP is interrupted. A TEAE leading to death is a TEAE for which the outcome is fatal. Relationship to IP is based on the investigator's causality judgment; that is, a drug-related AE is an AE indicated by the investigator to have a suspected relationship to IP.

#### 5.3 Baseline Definitions

For both efficacy and safety analyses in the Placebo-controlled Phase, baseline will be the last value measured prior to or on the day of the first dose of IP.

For safety analyses in Apremilast-exposure Period, baseline will be the last value measured prior to or on the first apremilast dose date.

#### 5.4 Time Points

Time points in all efficacy analyses are based on the visits/study weeks as recorded in the database. Appropriate dates (e.g., date of measurement or date of specimen collection) will first be used to ensure only data (including data from scheduled, unscheduled and discontinuation) measured or collected within the specific analysis phase/period are included, and then the visits/study weeks as recorded in the database will be used to assign one value (possibly missing) to each time point at the subject level. Only scheduled visit will be used for time point analysis.

#### Early Termination Visit

A value from the Early Termination Visit (for a discontinued subject) will be mapped to the subsequent scheduled visit for that parameter after the last visit the subject has completed.

Note that each measurement collected at the Early Termination Visit will only be mapped to the next scheduled visit for that measurement. For example, SF-36 is scheduled to be

Protocol Number: 20200058

Date: 07 February 2023

Page 32 of 67

collected at Week 16/Visit 5, Week 24/Visit 6, and Week 48/Visit 9. If a subject discontinued after Week 24/Visit 6, then the SF-36 Early Termination data would be mapped to Week 48/Visit 9, not Visit 7.

Analysis visits in safety analyses are based on the remapped visits/study weeks using the visit mapping algorithm (Appendix A), which may or may not be the same as the visits/study weeks as recorded in the database.

#### 5.5 Analysis Phases/Period

For the purposes of data analysis and reporting, below analysis phases/period for post-baseline data are defined: the Placebo-controlled Phases (through Week 24 and through Week 16) and the Apremilast-exposure Period.

The start and stop dates of each analysis phases/period are defined below, unless otherwise defined for a specific analysis or summary. Analyses for a specific period will include all data occurring, measured or collected (based on date of occurrence or measurement, or date of specimen collection, as appropriate) between the start and stop dates (inclusive or exclusive, depending on the data type) of that analysis phases/period. The specific rules for including or excluding the start and stop dates, depending on the data type, are also given below.

- Placebo-controlled Phase through Week 24:
  - Start date: The date of the first dose of IP.
  - Stop date:
    - The date of the first Week 16/Visit 5 dose for placebo-treated subjects who escape early at Week 16/Visit 5 and take at least one dose of IP dispensed at that visit, or
    - The date of the first Week 24/Visit 6 dose for subjects who complete Week 24/Visit 6, except for placebo-treated subjects who escape early, or
    - For all other subjects (i.e., subjects who discontinue prior to Week 24/Visit 6, with the exception of placebo-treated subjects who discontinue after early escape and has taken at least one dose of IP dispensed at Week 16/Visit 5), the date of the last study visit (including the Early Termination Visit and the Observational Follow-up Visit; i.e., all data after the start date will be included) for efficacy analyses, or 28 days after the last dose of IP or the date of death (if applicable), whichever comes first, for safety analyses.

Protocol Number: 20200058
Date: 07 February 2023
Page 33 of 67

Placebo-controlled Phase through Week 16:

- Start date: The date of the first dose of IP.

Stop date:

- The date of the first Week 16/Visit 5 dose for placebo-treated subjects who escape early at Week 16/Visit 5 and take at least one dose of IP dispensed at that visit, or
- The last non-missing Week 16/Visit 5 date for subjects who complete Week 16/Visit 5, except for placebo-treated subjects who escape early, or
- For all other subjects (i.e., subjects who discontinue prior to Week 16/Visit 5), the date of the last study visit (including the Early Termination Visit and the Observational Follow-up Visit; i.e., all data after the start date will be included) for efficacy analyses, or 28 days after the last dose of IP or the date of death (if applicable), whichever comes first, for safety analyses.

For the Placebo-controlled Phases, the start date is exclusive, and the stop date is inclusive for efficacy analyses, and safety analyses of laboratory, vital signs, weight, and ECG data. For AE analyses, the start date is inclusive, the stop date under the first 2 bullets is exclusive and the stop date under the third bullet is inclusive.

- Apremilast-exposure Period:
  - Start date:
    - The date of the first dose of apremilast after being randomized (at Week 0/Visit 2) or escaped/transitioned (at Week 16/Visit 5 or Week 24/Visit 6) to an apremilast dose group.
  - Stop date:
    - For efficacy analyses, the date of the last study visit available in the database (including the Early Termination Visit and the Observational Follow-up Visit; i.e., all data after the start date of the Apremilast-exposure Period will be included), or
    - For safety analyses, 28 days after the last dose of apremilast or the date of death (if applicable), whichever comes first, for subjects who have completed the study or have discontinued early by the time of database cut. For ongoing subjects, the data cutoff

Protocol Number: 20200058
Date: 07 February 2023
Page 34 of 67

date for safety analyses of laboratory, vital signs, weight, and ECG data, and AE analyses.

For the Apremilast-exposure Period, the start date is exclusive and the stop date is inclusive for efficacy analyses, and safety analyses of laboratory, vital signs, weight, and ECG data. For AE analyses, both the start and stop dates are inclusive.

#### 6. Analysis Sets

#### 6.1 Full Analysis Set

The Full Analysis Set (FAS) will consist of all subjects who are randomized as specified in the protocol. Subjects who are randomized in error and do not receive any dose of IP will be excluded from FAS. Efficacy analyses for the Placebo-controlled Phase will be primarily based on the FAS and subjects will be included in the treatment group to which they are randomized.

#### 6.2 Safety Analysis Set

The Safety Analysis Set will consist of all subjects who receive at least one dose of study medication. The safety analyses for the Placebo-controlled Phase will be based on the Safety Analysis Set and subjects will be included in the treatment group for the treatment they actually receive. For most subjects this will be the treatment group to which they are randomized. Subjects who take an IP that differs from the assigned one, according to the randomization schedule, for the entire Placebo-controlled Phase will be included in the treatment group corresponding to the IP they actually received. Subjects received at least one dose of apremilast in the Placebo-controlled Phase will have their actual treatment arm as apremilast.

#### 6.3 Per Protocol Set(s)

The Per Protocol (PP) Set will consist of all subjects who are randomized and receive at least one dose of study medication and have no major protocol deviations during the Placebo-controlled Phase that will have a major impact on the assessment of the primary endpoint. The final determination of major protocol deviations will be made prior to the unblinding of treatment assignment and will be documented. The PP analyses in the Placebo-controlled Phase will be based on the PP population and subjects will be included in the treatment group for the treatment they are randomized.

# 6.4 Health-related Quality-of-Life or Health Economics Analyses Set(s) Not applicable.

Protocol Number: 20200058 Date: 07 February 2023

# 6.5 Pharmacokinetic/Pharmacodynamic Analyses Set(s)

Not applicable.

# 6.6 Interim Analyses Set(s)

Not applicable.

#### 6.7 Study-specific Analysis Sets

#### 6.7.1 Apremilast Subjects as Randomized or Transitioned Population

The efficacy analyses for the Apremilast-exposure period that include data from the placebo-controlled and active-treatment extension phases will be based on the subjects as randomized or transitioned population, which will include all FAS subjects who are randomized (at Week 0) or escaped/transitioned (at Week 16 or Week 24) to apremilast. The data summaries will be tabulated by the group subjects are randomized to (i.e., separately for subjects who are randomized to apremilast or placebo at Week 0).

## 6.7.2 Apremilast Subjects as Treated Population

Safety analyses for the Apremilast-exposure Period will be based on the apremilast subjects as treated, which will include all subjects who are treated with apremilast from Week 0 or transitioned to apremilast at Week 16 or Week 24. Subjects' safety data during the Apremilast-exposure Period will be included.

#### 7. Planned Analyses

#### 7.1 Interim Analysis and Early Stopping Guidelines

No interim analysis will be conducted.

## 7.2 Primary Analysis

After all subjects have completed the Week 24 Visit (or discontinued from the study), a Week 24 database restriction will be performed, the primary data analysis will be conducted. However, unblinded data will only be made available to selected Sponsor and Contract Research Organization (CRO) team members involved with analysis of the data. All other Sponsor, site, and CRO personnel directly involved with the conduct of the study, will remain blinded to treatment assignments until the final database lock at the conclusion of the study.

The primary analysis will present data from the completed placebo-controlled phase of the study, including the primary, secondary endpoints at Week 16, and and safety results up to week 24.

Page 35 of 67

Protocol Number: 20200058
Date: 07 February 2023
Page 36 of 67

# 7.3 Final Analysis

At the end of the study, after all subjects have completed or have been discontinued from the Apremilast Extension Phase (Weeks 24 to 48) and the Observational Follow-up Phase, the final analysis will be performed. The scope of the final analysis is the evaluation of the long-term efficacy and safety data. A final Clinical Study Report will be generated.

#### 8. Data Screening and Acceptance

#### 8.1 General Principles

The objective of the data screening is to assess the quantity, quality, and statistical characteristics of the data relative to the requirements of the planned analyses.

#### 8.2 Data Handling and Electronic Transfer of Data

The Amgen Global Study Operations-Data Management (GSO-DM) department will provide all data and will be processed by Amgen Global Statistical programming (GSP) to be used in the planned analyses. This study will use the RAVE database, the efficacy endpoint data received from Clario (formerly ERT), IWRS data from Endpoint and Laboratory data from LabCorp (formerly Covance).

#### 8.3 Handling of Missing and Incomplete Data

#### 8.3.1 Adverse Events

Partially missing AE start dates will be imputed in the ADaM dataset for AEs.

#### Adverse Events

Partially missing AE start dates will be imputed in the ADaM dataset for AEs, but partially missing AE end dates will not be imputed in the same dataset. If the AE end date is complete with no missing year, month, or day, and the partially missing start date imputed by the rules below is after the AE end date, then the start date will be imputed by the AE end date.

#### Subjects who were treated with apremilast at Week 0/Visit 2

The principle of the imputation rules for subjects who were treated with apremilast initially is to treat the AE as treatment-emergent, i.e., occurring on or after the date of the first dose of IP, if possible.

Let an AE start date be represented as " $D_{Event}/M_{Event}/Y_{Event}$ ", and the date of the first dose of IP as " $D_{IP}/M_{IP}/Y_{IP}$ ". The following table gives the imputation rules for partially missing AE start dates for subjects who were treated with apremilast initially.

Protocol Number: 20200058 Date: 07 February 2023

Table 2. Imputation Rules for Partially Missing AE Start Dates for Subjects Who Were Treated with Apremilast Initially

Scenario	Condition	Imputation Rule
Partially missing date includes year only (Both month and day are missing)		
1	$Y_{Event} < Y_{IP}$	12/31/Y Event
2	Otherwise	Max(day of first dose of IP, 1/1/Y Event )
Partially missing date includes both year and month (Only day is missing)		
1	$Y_{Event} < Y_{IP}$ , or $(Y_{Event} = Y_{IP})$	Last date of M Event /Y Event
	and M Event <mIP)</m	
2	Otherwise, i.e., Y IP < Y Event ,	Max (date of first dose of IP,
	or (Y IP =Y Event and M IP ≤	1/M Event /Y Event )
	M Event )	

#### Subjects who were treated with placebo at Week 0/Visit 2

The principle of the imputation rules for subjects who were treated with placebo initially and started apremilast treatment at Week 16 or Week 24 is to consider the AE starting on or after the date of the first dose of apremilast, if possible; if the partially missing start date suggests that it is prior to the date of the first dose of apremilast, the AE will be considered starting on or after the date of the first dose of IP, if possible.

The following are 4 scenarios considered in the imputation rules:

- The partially missing AE start date suggests the date is prior to the date of the first dose of IP: impute it by the latest possible date (determined by the nonmissing field of the date);
- The partially missing AE start date suggests the date is after the date of the first dose of apremilast: impute it by the earliest possible date (determined by the non-missing field of the date);
- 3. The partially missing AE start date is in the same year (if both month and day are missing), or the same year/month (if only day is missing) of the first dose of apremilast: impute it by the date of the first dose of apremilast;
- 4. The partially missing AE start date suggests the date is no earlier than the date of the first dose of IP but prior to the date of the first dose of apremilast: impute it by the date of the first dose of IP, or the earliest possible date (determined by the non-missing field of the date), whichever occurs later.

Page 37 of 67

Protocol Number: 20200058

Date: 07 February 2023

Page 38 of 67

Let an AE start date be represented as " $D_{Event}/M_{Event}/Y_{Event}$ ", the date of the first dose of IP as " $D_{IP}/M_{IP}/Y_{IP}$ ", and the date of the first dose of apremilast following Week 24 or early escape date as " $D_{APR}/M_{APR}/Y_{APR}$ ". The following table gives the imputation rules for partially missing AE start dates.

Table 3. Imputation Rules for Partially Missing AE Start Dates for Subjects Who Were Treated with Placebo Initially

Scenario	Condition	Imputation Rule	
Partially missing date includes year only (Both month and day are missing)			
1	Y Event < Y IP	12/31/Y Event	
2	Y Event > Y APR	1/1/Y Event	
3	$Y_{Event} = Y_{APR}$	Date of first dose of apremilast	
4	Otherwise, i.e., Y IP ≤ Y Event <	Max (date of first dose of IP, 1/1/Y Event )	
	Y APR		
Partially missir	ng date includes both year and r	month (Only day is missing)	
1	$Y_{Event} < Y_{IP}$ , or $(Y_{Event} = Y_{IP})$	Last date of M Event /Y Event	
	and M Event <mIP)</m		
2	$Y_{Event} > Y_{APR}$ , or $(Y_{Event} = Y_{APR})$	1/M Event /Y Event	
	and M Event > M APR )		
3	Y Event = Y APR and M Event =	Date of first dose of apremilast	
	M APR		
4	Otherwise, i.e., Y IP < Y Event <	Max (date of first dose of IP,	
	$Y_{APR}$ , or $(Y_{IP} = Y_{Event} < Y_{APR})$	1/M Event /Y Event )	
	and M IP ≤ M Event ),		
	or		
	$(Y_{IP} = Y_{Event} = Y_{APR} \text{ and } M_{IP} \le$		
	$M_{Event} < M_{APR}$ , or $(Y_{IP} < Y_{Event})$		
	= Y APR and M Event < M APR )		

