#### 9.6.2 Adverse Events

The Medical Dictionary for Regulatory Activities (MedDRA) version 25.1 or later will be used to code all events categorized as adverse events to a system organ class and a preferred term with SOCs presented in the standard international order and PTs within SOCs will be presented in descending order of subject incidence.

The subject incidence of adverse events will be summarized for all treatment-emergent adverse events, drug-related treatment-emergent adverse events, severe adverse events, serious adverse events, adverse events leading to discontinuation of investigational product, fatal adverse events and adverse events of interest.

Protocol Number: 20200058

Date: 07 February 2023

Page 56 of 67

A subject data listing of all AEs (including TEAEs and non-TEAEs) will be provided.

An overall summary of the following AE categories will be provided:

- Any TEAE
- Any drug-related TEAE
- Any severe TEAE
- Any serious TEAE
- Any serious drug-related TEAE
- Any TEAE leading to drug interruption
- Any TEAE leading to drug withdrawal
- Any TEAE leading to death

Summarization of the following AE categories will be provided:

- Any TEAE (by SOC and PT, and by PT only)
- Common TEAE (subject incidence ≥ 5% by SOC and PT, and by PT only)
- Any serious TEAE (by SOC and PT)
- Any non-serious TEAE (by SOC and PT)
- Any drug-related TEAE (by SOC and PT)
- Any serious drug-related TEAE (by SOC and PT)
- TEAEs by maximum severity (by SOC and PT)
- Any TEAE leading to study drug withdrawal (by SOC and PT)
- Any TEAE leading to study drug interruption (by SOC and PT)
- Any TEAE leading to death (by SOC and PT), if applicable

If a subject reports multiple occurrences of a specific event within a specific analysis phase/period, the subject will be counted only once by the maximum severity (mild, moderate, severe, and, if needed, missing). If the severity is missing for one or more of the occurrences, the maximum severity of the remaining occurrences will be used. If the severity is missing for all occurrences, the subject will be counted only once in the "missing" category of severity.

Protocol Number: 20200058

Date: 07 February 2023

Page 57 of 67

The relationship of an AE to IP is recorded on the AE CRF page as "not suspected" and "suspected". Adverse events recorded as "suspected" or with missing relationship to IP will be assessed as drug-related.

Summaries about selected TEAEs will also be provided by onset day and the event duration.

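### Partial adverse-event start dates are imputed by initial arm, which puts a small, artificial difference against apremilast into the placebo-controlled AE tables and stacks imputed dates on Day 1

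*SAP*

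**What the plan says.** SAP 8.3.1 has one set of rules for subjects who start on apremilast and another for subjects who start on placebo.

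- **Apremilast starters (Table 2).** The principle "is to treat the AE as treatment-emergent, i.e., occurring on or after the date of the first dose of IP, if possible". Unless the partial date is clearly before first dose, it becomes the later of the first IP dose and the earliest date that the known fields allow.
- **Placebo starters who switch at Week 16 or 24 (Table 3).** The principle "is to consider the AE starting on or after the date of the first dose of apremilast, if possible". Under scenario 3, when the partial date shares the year, or the year and month, of the first apremilast dose, the instruction is to "impute it by the date of the first dose of apremilast". Under scenario 4, when the date is clearly before the switch, it is to "impute it by the date of the first dose of IP, or the earliest possible date", whichever is later. Scenario 4 gives the same result as Table 2.
- **Both arms.** If the AE end date is complete and falls before the imputed start, the start is reset to the end date.

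SAP 5.5 ends the Placebo-controlled Phase at the first Week 16 dose for placebo early escapers and at the first Week 24 dose for other completers. For AE analyses "the stop date under the first 2 bullets is exclusive". SAP 9.6.1 presents placebo-controlled safety by treatment group. SAP 9.6.2 adds that "Summaries about selected TEAEs will also be provided by onset day and the event duration", together with new events by exposure interval starting at 1 week or less.

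**The concern.** For a placebo switcher the first apremilast dose is also the phase stop date, and it is excluded. Scenario 3 therefore moves the event out of the placebo column into the Apremilast-exposure Period. The same recorded date in an apremilast starter usually remains in the phase, and can even bring in an event that truly began in the extension. Nothing in the SAP limits Table 3 to the Apremilast-exposure tables, and no sensitivity analysis covers it. Part of any between-arm difference in AE incidence would then come from the imputation rule.

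Timing is affected as well. A partial date in the first-dose month or year becomes Day 1 under Table 2. A scenario 3 date becomes apremilast Day 1 in the Apremilast-exposure Period. Both feed the onset-day and first-week summaries. SAP 9.6.1 also gives an event on the first dose day an exposure time of 1 day, which shortens the EAIR denominator.

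**Working it through.** The plan states no figure on this point, so there is nothing to reproduce first.

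**Worked example.** First IP dose 10 Feb 2021; Week 24 dose 168 days later, 28 Jul 2021.

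| Recorded start | Apremilast starter | Placebo switcher |
|---|---|---|
| 2021 only | 10 Feb: in phase | 28 Jul: out |
| Jul 2021 | 1 Jul: in phase | 28 Jul: out |
| Apr 2021 | 1 Apr: in phase | 1 Apr: in phase |

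**Share of true phase events lost by placebo.** Assumptions: onset uniform over the phase, first-dose dates uniform over a 365-day year, no complete end date.

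- *Day missing.* Events on days of the switch month before the switch are lost. The mean number of such days is (7×465 + 4×435 + 378)/365 = 14.72. Week 24 switch: 14.72/168 = 8.8% lost, 91.2% kept. Week 16 escape: 14.72/112 = 13.1% lost, 86.9% kept.
- *Month and day missing.* Phase days in the same calendar year as the switch are lost. Week 24: (168×167/2 + 168×197)/(365×168) = 76.8% lost, 23.2% kept. Week 16: (112×111/2 + 112×253)/(365×112) = 84.5% lost, 15.5% kept.

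Apremilast starters keep 100%, because the earliest possible date is never later than the true one. They also gain extension events: 8.8% of those with the day missing and 76.8% of the year-only ones, against 0% for placebo. This gain needs the extension events to be in the database at the cut.

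**Effect of the end-date reset** (Week 24 switch, complete end date):

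| Event length | Day missing, placebo keeps | Year only, placebo keeps |
|---|---|---|
| 7 days | 96.4% | 95.9% |
| 28 days | 91.3% | 84.0% |

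The reset does not reduce the gain on apremilast, where the imputed start is early.

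**Overall size.** The frequency of partial dates is not given. Assume 5% of AEs lack the day and 1% lack day and month, with identical AE processes in both arms over 48 weeks.

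- Apremilast count / true count: 0.94 + 0.05×1.088 + 0.01×1.768 = 1.012.
- Placebo, no end dates: 0.94 + 0.05×0.912 + 0.01×0.232 = 0.988. Ratio 1.024.
- Placebo, all events 7 days with known end: 0.94 + 0.05×0.964 + 0.01×0.959 = 0.998. Ratio 1.014.

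**On the incidence scale.** Take the 42.9% placebo TEAE incidence from the earlier pooled studies (protocol 1.2.1.2.1), one AE per subject and no end dates. The fall in placebo incidence is 42.9 × share partial × share lost:

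| Share of AEs with partial start | Day missing | Year only |
|---|---|---|
| 1% | 0.04 points | 0.33 points |
| 5% | 0.19 points | 1.6 points |
| 10% | 0.38 points | 3.3 points |

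With about 285/3 = 95 placebo subjects, 0.19 points is about 0.2 of a subject.

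**The case against.** **The effect is small and conservative.** The rule under-counts placebo events and can over-count apremilast events, so it works against the study drug. Safety is descriptive and no efficacy endpoint is touched. AEs are collected at every visit and the protocol requires start and stop dates, so year-only dates for on-study events should be rare. Dates clearly before the switch are treated alike. Day-1 stacking of day-missing dates from the first-dose month is also the same in both arms within the Placebo-controlled Phase. All of this stands, and it limits the point to a refinement.

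**Applying Table 2 to both arms could misplace real drug effects.** Placebo switchers begin apremilast titration at the switch, and protocol 6.5.5 says most diarrhea is reported in the first 2 weeks of treatment. Over 16 weeks, diarrhea was 13.2% on 30 mg BID and 2.5% on placebo (protocol Table 8). Assume half of apremilast diarrhea starts uniformly in the first 14 days and the switch day is uniform in a 30-day month. Post-switch onset in that month is then 13.2% × 0.5 × (1 − 7/30) = 5.1%. Pre-switch onset is 2.5%/112 × 15 = 0.33%. About 94% of switch-month diarrhea is then truly on apremilast; with one tenth instead of half, about 75%. Scenario 3 places these events correctly, and Table 2 would move most of them into the placebo column. This also stands. It rules out simply replacing Table 3.

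Neither objection removes the asymmetry in the randomised comparison or the Day-1 stacking.

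**Conclusion.** The arm-dependent rule is real and follows directly from SAP 8.3.1 read with 5.5. It creates a small difference against apremilast in the placebo-controlled AE tables. It is confined to dates overlapping the switch month or year, and the loss from placebo falls mainly on ongoing or long events and those without a complete end date. On the assumed 5% and 1% rates the relative excess is about 2% or less. That rests on year-only dates being rare, which the documents do not quantify.

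A reader might infer more. The year-only figures give a ratio of 1.768/0.232 = 7.6, but only among year-only events with no complete end date; it does not describe the overall comparison. Nor do the documents support reading the rule as hiding apremilast harm, since its direction is the opposite, or as sending every apremilast partial date to the first dose: a later month with only the day missing goes to the first of that month.

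The distortion of the onset-day, first-week and EAIR results holds whichever arm it favours.

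**What to change.** Keep Tables 2 and 3 as the main, conservative convention and add two items to the SAP before unblinding.

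1. Report the number of imputed AE start dates by arm, split into day missing and month and day missing. Repeat the main Placebo-controlled Phase TEAE tables as a sensitivity analysis with one arm-neutral rule, for example Table 2 relative to first IP dose in both arms. Footnote that this rule can move post-switch events into the placebo column, and that such an event may also appear in the Apremilast-exposure tables.
2. Leave imputed start dates out of the onset-day and exposure-interval summaries, or show them in a separate row.

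The cost is a few extra tables, one extra derived date variable and the SAP wording. No data collection or efficacy analysis changes.
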